Recruitment. We will mail recruitment materials to individuals identified as eligible based on ICD10 codes inviting them to participate in a VA research study aimed at helping Veterans who experience chronic low back pain. We will require real SSN access to pull Veteran demographic, health and contact information for recruitment efforts. Patients will receive a recruitment letter and flier in the mail and will be asked to contact our study team if they are interested in participating. As needed, we may also place follow-up telephone calls to Veterans who do not contact us. If needed, we will also employ the following recruitment strategies: we will post fliers in primary care and pain clinic waiting areas; we will ask providers working in primary care and pain clinics to refer eligible Veterans to the study; we will have our project coordinator recruit in person in pain clinic waiting areas; we will ask Veterans who enrolled and participated in early classes to refer their peers to the study (i.e., snowball sampling). Veterans who are interested will contact our project manager, who will screen them for eligibility based on the inclusion criteria detailed below using a screening form. If we receive responses from primarily women Veterans early in our recruitment efforts, we will target later recruitment efforts to male Veterans to ensure that both male and female Veterans are represented in the study.

Randomization. Eligible patients will be randomly assigned to RAP or treatment as usual (regular yoga routinely offered at the hospital, which at our facility is Hatha yoga) using a random number generator.

Intervention Details. Both the RAP and Hatha yoga classes will be offered once a week for 12 weeks; this 'dose' of yoga has been found to be effective in a previous randomized controlled trial (RCT) focused on yoga participation among individuals with back pain.¹ Classes will be about 60 minutes long. To accommodate targeted class sizes, we will run two cohorts, either concurrently (on different days of the week) or in waves (one session held after the first is completed) if needed. Yoga mats, straps and sets of blocks will be available for participants to use.

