Enrollment and Sample Size. As mentioned above, we will aim to enroll 16-20 Veterans in RAP and another 16-20 Veterans in the Hatha yoga program, for a total recruitment target of 32-40 Veterans. Looking back 3 months, we estimate that there are approximately 1,500 Veterans at Hines who meet our study eligibility criteria. Accordingly, we do not anticipate having any difficulties identifying and enrolling enough patients to meet this target. However, if needed we will expand our time-frame to include Veterans who received the

relevant diagnoses in the previous 6, 9 or 12 months. Of note, goals for aims 2 and 3 include determining feasibility numbers for recruitment and estimates of effect sizes to inform power considerations for the next step, the larger trial.

Data Collection. Our data collection instruments reflect the factors that influence behavior as outlined in our conceptual framework; the relevant factors are noted in *italics* next to relevant questions in the appendices. Outcomes and strategies for measuring each are described below and summarized in Table 1.

Pre- and Post- Program Participation Surveys. All Veterans who are enrolled into the study will receive a pre-participation survey (Appendix D) approximately 1 week before the RAP/Hatha yoga classes begin, and a post-participation survey approximately 1 week after the 12-week programs are finished (Appendix E). Surveys will be mailed to Veterans so that persons who do not attend the first class of the program they are randomized to or do not complete

the program still have the opportunity to fill out a survey. This will allow us to also compare outcomes between individuals who did and did not complete the programs. Veterans will also be given the option to complete the surveys over the phone with the study project manager, and we will follow up with Veterans who do not return a mailed survey by phone to

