optimize response rates. We will also provide Veteran to complete the baseline survey in-person at the time of study enrollment. Veterans who attend the first and last yoga class of each session will also be provided an opportunity to complete the survey in person at their preference. Veterans will receive \$25.00 in appreciation of their time for each returned survey (up to two total surveys). Of note, we will not provide any token incentives for completing the yoga programs because we do not want to contaminate adoption rate data such that we cannot tease out whether Veterans are participating because they like the program or because they want to complete the program so that they can earn the incentive.

The surveys will include measures of pain intensity; pain behavior; function; quality of life (QOL); sleep; depression; stress; medication (and other pain reduction strategy) use, and; patient perceptions of and experiences with the program.

Pain intensity will be measured using the Defense and Veterans Pain Rating Scale,⁵ a valid and reliable numeric rating scale that asks individuals to report the average intensity of their low back pain on a scale of 0 (no pain) to 10 (worst pain imaginable)⁶ for the previous 7 days.

Pain interference (how much the individual's pain has interfered with all aspects of their life in the prior 7 days) will be measured using the validated, reliable Patient-Reported Outcomes Measurement Information System (PROMIS) 8-item pain interference short form.⁷ PROMIS scores are standardized to reflect the general adult US population, such that a mean score of 50 reflects average pain experience; higher scored indicate greater levels of pain interference.

Back pain-related function will be measured using the Roland-Morris Disability Questionnaire (RMDQ), a valid and reliable scale of physical disability resulting from chronic low back pain.⁸ The RMDQ asks individuals to read 24 items noting back pain-related functional impairments and mark those that describe them. All marked items are summed for a total score ranging from 0 (no impairment) to 24 (maximum impairment). A 30% reduction in score from baseline coupled with an improved self-reported pain intensity rating is considered a clinically significant impact.⁹

Health-related QOL will be measured using the Medical Outcomes Study 12-Item Short Form Health Survey (SF-12),¹⁰ a valid and reliable measure that produces physical and mental health sub-scale scores.

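### Baseline surveys may be completed at the first class, after allocation is known, and optional last-class post surveys fall about 7–14 days before the planned date

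*Combined protocol and SAP*

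**What the plan says.** Under Pre- and Post- Program Participation Surveys, the baseline for each enrolled Veteran is planned as "a pre-participation survey (Appendix D) approximately 1 week before the RAP/Hatha yoga classes begin". For follow-up, the plan in the same section is "a post-participation survey approximately 1 week after the 12-week programs are finished". Surveys go out by mail so that people who "do not attend the first class of the program they are randomized to", or who drop out later, can still respond. The protocol adds: "This will allow us to also compare outcomes between individuals who did and did not complete the programs".

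Other routes are offered to raise response:

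- Telephone completion is available, and "we will follow up with Veterans who do not return a mailed survey by phone".
- In-person completion is also possible on class days: "Veterans who attend the first and last yoga class of each session will also be provided an opportunity to complete the survey in person".
- As a further route, a Veteran may "complete the baseline survey in-person at the time of study enrollment".

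Under Randomization, "Eligible patients will be randomly assigned to RAP or treatment as usual". That section gives no date for allocation or its disclosure, and does not make a completed baseline a condition of either. The Program Initiation and Participation section writes enrollment and randomization as one step, and defines starting a program as something that happens after randomization.

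Under Quantitative Analysis of Surveys, outcomes are compared before and after participation and between the two programs. Effect sizes on key outcomes, including pain intensity, pain interference and back function, are to drive the power calculation for the next trial.

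**The concern.** Participants know which class they are in, and the outcomes at issue are self-reported. RAP was designed around how Veterans perceive yoga, so learning the assignment could plausibly colour answers, and could do so differently in the two arms. A baseline given after that moment may partly measure a reaction to the assignment. It would then feed into every pre-post change and into the 30% reduction on the Roland-Morris questionnaire that the protocol treats as part of a clinically significant impact.

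The last-class option raises a separate issue of timing and setting. Pain intensity and interference refer to the past 7 days, and sleep and depression to about the past two weeks. A survey at the last class looks back on weeks when classes were running. A survey on the planned date looks back partly or wholly on time after they ended. Only those present at the last class can use this route, so timing can vary with attendance. It could also vary by arm if engagement is higher in RAP, as the protocol hypothesizes.

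**Working it through.** **1. Does a first-class baseline follow allocation?** The in-person sentence says only that the survey may be completed at the first and last class. The natural reading is baseline at the first and post survey at the last. The same section describes the first class as that of the program to which the Veteran was randomized. A baseline completed there is therefore post-allocation. Nothing says it must be finished before that class starts.

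**2. Are the other routes tied to allocation?** The mailed survey is timed to the start of classes. The telephone route has no date of its own. The enrollment route has no stated order relative to randomization. The text therefore neither requires nor rules out baseline first for these routes.

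**3. How early is a last-class post survey?** Inputs: weekly classes for 12 weeks (Intervention Details), and a session being a full 12-week run (Class Size). Set the first class at day 0.

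- Last class: 7 × 11 = day 77.
- If the program finishes at the last class, the planned post survey is 77 + 7 = day 84, a gap of 84 − 77 = 7 days.
- If it finishes after 12 full weeks, the planned post survey is 84 + 7 = day 91, a gap of 91 − 77 = 14 days.
- Planned pre-to-post interval, from day −7: 91 or 98 days. First class to last class: 77 days.

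The planned times are approximate, and mailed surveys may come back later still.

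**4. Can the bias be sized?** Suppose the between-arm analysis uses change scores. The baseline contribution is then, in absolute value, |p_R·s_R − p_H·s_H|, where p is the share of post-allocation baselines in an arm and s the mean shift they carry. The post-survey contribution is the difference between arms in last-class share, multiplied by the shift due to timing and setting. The documents give none of these quantities. The first expression is zero when shares and shifts match across arms, and the second when last-class shares match. The two may add or offset.

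**5. How does it compare with sampling error?** Use SE(d) = √(2/n + d²/(4n)), with n = 16–20 per arm from the protocol and d = 0.40 assumed.

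- n = 20: √(0.100 + 0.002) = 0.32.
- n = 16: √(0.125 + 0.0025) = 0.36.

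For the baseline contribution alone to equal one standard error, with the same share p in both arms, the arms' shifts would have to differ by SE/p:

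| Assumed p | Difference in shifts needed (SD) |
|---|---|
| 25% | 0.32/0.25 = 1.28 to 0.36/0.25 = 1.44 |
| 50% | 0.64 to 0.72 |
| 100% | 0.32 to 0.36 |

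These are break-even values, not estimates of bias.

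**6. What would an analysis without post-allocation baselines show?** If 25% were excluded (assumed), 12–15 per arm would remain. SE(d) would be √(2/15 + 0.16/60) = 0.37 to √(2/12 + 0.16/48) = 0.41. That is too imprecise to confirm or exclude a modest bias.

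**The case against.** The case for leaving the plan alone has real force. Both arms get the same survey options. The several routes exist to protect response, a fair trade with 32–40 Veterans. Reach and engagement, the primary focus, are tracked by sign-in at each class. All of this stands, and it limits the importance of the point.

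Four stronger readings are tempting and are not supported:

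- A reader might infer that the plan lets every baseline follow allocation. Only the first-class route is established. Figure 2, which the Design Overview cites for data collection, was not available and may give the order for the others. Appendices D and E were not available either and may already carry a date field.
- A reader might infer that the RAP–Hatha comparison must be biased through baseline. The analysis section names t-tests and ANOVA but does not say whether the between-program comparison uses change scores or baseline adjustment. If it compares post scores alone, this route contributes nothing.
- A reader might attach a figure to the bias, or to the resulting sample size of the next trial. Any such figure would rest entirely on invented shares and shifts.
- A reader might take the completer comparison as the main casualty. It is non-randomized and open to selection whatever the survey date. Completion also means 9 of 12 classes, so a completer can miss the last class and a non-completer can attend it.

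What remains is an express permission to take baseline after a known assignment, in an unblinded study whose self-reported effect sizes are to be reused. A confidence interval would not reflect that error, and without dates and modes it could not be examined.

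**Conclusion.** The point holds in a limited form and is one to consider rather than a necessary change. It is firm on the wording that a first-class baseline follows allocation, and on the arithmetic that a last-class post survey falls about 7–14 days early. Both assume the natural reading of the in-person sentence.

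The exposure is confined to the self-reported pre-post changes, the between-program comparison if it uses baseline, and the effect sizes passed to the larger trial. Post-survey timing adds a smaller uncertainty tied to attendance. That the bias is probably smaller than sampling error is a judgement, supported by the break-even values above. No numeric bias or planning range should be relied on.

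**What to change.** - Make completion of the baseline survey before allocation is disclosed the default, at enrollment or by phone or mail, using the follow-up calls already planned.
- Keep the first class only as a fallback for Veterans with no baseline. The survey should be completed before that class starts and flagged as post-allocation. Do not withhold allocation or class entry, so that reach is unaffected. Removing the fallback altogether could push some baselines past first exposure to the program.
- Record completion date and mode for every survey, if the forms do not already do so, and report both by arm and by completer status.
- Repeat the outcome analyses without post-allocation baselines, as a descriptive check only.
- The last-class post option may stay, since it protects response.

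The cost is minor protocol wording and at most two data fields, with no extra visits. The downsides are some extra reminder calls, tighter scheduling before classes start, and slightly later notice of class assignment. The last matters most if cohorts run on different days of the week.

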Rage Against the Pain. The RAP program curriculum will mirror that of the Hatha Yoga classes, but will differ from this traditional yoga practice in a number of ways: (1) the classes will be set to rock/heavy metal music; (2) meditation will not be incorporated; (3) yoga terms will not be used to describe the poses/movements (rather, poses will be cued in plain descriptive English terms); (4) the culminating activity for the class will be called a 'cool down' (rather than the typical relaxation/meditation exercise used in yoga, referred to as savasana).

Possible Risks or Discomforts. Any procedure has possible risks and discomforts. The procedures in this study may cause all, some, or none of the following risks or side effects: participating in the Rage Against the Pain High Intensity Stretching or Hatha Yoga classes may cause muscle soreness, pain, fatigue, injury, and/or emotional discomfort; participating surveys/semi-structured interviews may lead to discomfort with answering certain questions (Veterans will be informed that they do not have to answer any question(s) that make them feel uncomfortable). The recreation therapists running the intervention classes are trained and will make sure the class activities can be modified to make sure everyone can participate safely. Participants will be encouraged to participate at their own ability and not push past their limits. Our instructors are seasoned VA recreation therapists and have experience with working with Veterans who experience pain.

There is also a small risk of breach of confidentiality. We will take every possible step to protect the privacy of the study information, such as using a study ID rather than participant names for all data collection (surveys and interviews) and making sure research data are secure and computer files are password protected.

Risks of the usual care are not risks of the research. Those risks are not detailed in this protocol. During the consenting process, participants will be asked to talk with their health care providers if they have any questions about the risks of usual care. Participation in research may involve a loss of privacy. All research records will be kept as confidential as possible.

To mitigate any potential risks or discomforts, we have developed a comprehensive safety plan (please see below).

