Pose Modifications. Yoga instructors will cue options for modification of each pose. Veterans will be encouraged to participate at their own ability and not push past their limits. Our yoga instructors are seasoned VA recreation therapists, and have experience working with Veterans who experience pain.

Monitoring Adverse Events. We will meticulously monitor adverse events. Adverse events will be tracked in a number of ways: (1) all participants will be encouraged to discuss any impacts they believe program participation may be having on their health with the yoga instructors either before or after class each week – we will ask both the participants and yoga instructors to report this information to the study project manager, (2) we will include a question on the post-program follow-up survey to assess any perceived impacts of participation on Veterans' health, and (3) among Veterans who do not complete the follow-up survey or leave this question blank, the study project manager and/or PI will conduct a thorough chart review to rule out notation of possible study-related adverse events in the patient's medical record.

Right of the Investigator to Terminate Participation. We have the right to terminate a Veteran's participation, without regard to their wishes, in the research study if any of the following occur: (1) they become uncooperative or unwilling to complete study-related tasks; (2) they are experiencing undue stress from the study procedures; (3) they are experiencing undue physical strain from the study procedures (e.g., the exertion required is too great for them, participation is causing them excessive pain, etc.); (4) they have a substance abuse, mental health, and/or medical problem that interferes with completion of the study-related tasks; (5) they behave inappropriately in a session or while completing a study-related task; (6) the study is stopped by the sponsor, which is the VA Office of Research Development.

Follow-Up Care. If a Veteran experience injuries from their participation in this research project, we will either (1) get their permission to contact your Hines primary care provider and suggest that they follow up with the Veteran, or (2) escort the Veteran to the Hines Emergency Department, contact the Hines rapid response team (if you are within the area of their purview), or call 911. We will not be doing follow-up care with individuals who choose to withdraw from the study.

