We will ask participants to self-report any *pain medication use* (e.g., opiates, muscle relaxants, NSAIDs) in the pre- and post-participation surveys. Medication use will be corroborated through brief, targeted chart reviews, which reflects the process used by Groessl et al.³ to collect information about pain medication use for their RCT of yoga for low back pain among Veterans. We will also ask participants to report *any use of other programs for pain management* (e.g., acupuncture, massage, mindfulness/meditation, cognitive-behavioral therapy) on both the pre- and post-participation surveys. This information will also be corroborated through brief, targeted chart reviews. The surveys will also include some basic questions (that map to our conceptual model) about patient's *perceptions of and experiences with the program* (extent to which they liked it, would participate again, would recommend to a peer, felt it impacted their health and how); these topics will be assessed in-depth via the post-participation semi-structured interview.

Program Initiation and Participation. The primary focus of this study is the reach and sustained engagement of the RAP program, which we hypothesize will be greater compared to traditional (Hatha) yoga. *Program initiation* (e.g., reach) will be defined as the number of individuals who start the RAP or Hatha yoga programs after being screened, deemed eligible for participation, and randomized to one or the other.

Program participation (e.g., sustained engagement) will be defined as the average number of classes Veterans attended for each respective program, and the number of Veterans who attended the majority (9/12) of classes. These outcomes will be tracked via self-report (on the post-participation survey) and in real-time by asking Veterans to sign in before each class they participate in. In addition, we will ask any Veteran who contacts us indicating interest but ultimately chooses to not enroll in the study before they are enrolled/randomized why they are choosing not to participate.

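### Neither participant-reported adverse-event route is described as asking directly about harm, and a benefit-only survey answer does not trigger the chart review

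*Combined protocol and SAP*

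**What the plan says.** Monitoring Adverse Events sets out three routes.

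1. In class: "all participants will be encouraged to discuss any impacts they believe program participation may be having on their health with the yoga instructors", before or after each weekly session. Participants and instructors are both asked to pass this on to the project manager.
2. On the survey: "we will include a question on the post-program follow-up survey to assess any perceived impacts of participation" on the Veteran's health.
3. In the chart: "among Veterans who do not complete the follow-up survey or leave this question blank", the project manager or principal investigator will "conduct a thorough chart review to rule out notation of possible study-related adverse events".

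The Data Collection section lists, among survey topics on liking the program and recommending it, whether Veterans "felt it impacted their health and how". It adds that these topics are taken further at interview. Possible Risks or Discomforts states that the classes in either arm "may cause muscle soreness, pain, fatigue, injury, and/or emotional discomfort".

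**The concern.** An open question about effects allows a Veteran to mention a harm but does not prompt for one. Someone who strained a muscle in an early class and finished the program feeling better can truthfully answer that their back has improved. That answer is complete, so the chart review, which is the only route aimed specifically at adverse events, is not triggered.

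Harms would then be under-recorded mainly among Veterans who also felt some benefit. The protocol promises close monitoring of adverse events, and the pilot is meant to inform a larger trial. With 16-20 Veterans per arm, a few missed events can decide whether a program appears free of harm.

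**Working it through.** The protocol gives no figure for adverse events, so there is nothing to reproduce. The main check is a reading of the routes against each other.

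**Step 1: what each route asks, and of whom**

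| Route | Reaches | Directed at harm? |
|---|---|---|
| Talk with instructors | Everyone attending, weekly | No: neutral and volunteered |
| Survey question | Everyone returning the post survey | No: neutral, though a harm can be written in |
| Chart review | Only those with a missing survey or a blank answer | Yes |

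**Step 2: follow four Veterans, each with a harm, through the survey and the chart-review rule**

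| Survey outcome | Chart review? | How the harm is captured |
|---|---|---|
| Survey not returned | Yes | Chart, if noted there |
| Question left blank | Yes | Chart, if noted there |
| Answer mentions the harm | No | Survey |
| Answer mentions only a benefit | No | Only if volunteered elsewhere |

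The fourth row is the gap. The trigger depends on whether an answer exists and not on what it says.

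**Step 3: do other parts of the plan close the gap?**

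- The other chart reviews (Data Collection) cover medication and use of other pain programs only.
- Pain intensity and pain interference refer to the previous 7 days, sleep to 14 days and depression to two weeks. The post survey is given once, about 1 week after 12 weeks of classes. An injury that resolved mid-program could leave no trace in these scales, and none of them attributes a change to the classes.
- The example interview questions use the same neutral wording about effects. The interview is not listed as an adverse-event route.
- Table 1 has no adverse-event row, and Quantitative Analysis of Surveys names no adverse-event summary.

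**Step 4: sensitivity illustration**

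Inputs: n = 16 or 20 per arm (Enrollment and Sample Size). The harm rate r and the one-half masking are assumptions, not protocol figures. Veterans are treated as independent.

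P(no harm recorded in an arm) = (1 - r)^n with full reporting, and (1 - r/2)^n if half of the harmed Veterans go unrecorded.

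| r | Full, n = 16 | Full, n = 20 | Half masked, n = 16 | Half masked, n = 20 |
|---|---|---|---|---|
| 0.10 | 0.90^16 = 0.185 | 0.90^20 = 0.122 | 0.95^16 = 0.440 | 0.95^20 = 0.358 |
| 0.15 | 0.85^16 = 0.074 | 0.85^20 = 0.039 | 0.925^16 = 0.287 | 0.925^20 = 0.210 |
| 0.20 | 0.80^16 = 0.028 | 0.80^20 = 0.012 | 0.90^16 = 0.185 | 0.90^20 = 0.122 |

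At r = 0.15 the expected number of harmed Veterans per arm is 0.15 × 16 = 2.4 to 0.15 × 20 = 3.0. The chance of recording none is 4-7% with full reporting and 21-29% with half masked. Over r = 0.10 to 0.20 the ranges are 1-19% and 12-44%.

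**The case against.** A reader might infer that no route looks for harm, or that the pilot never asks about it. The documents do not support that.

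- The chart review explicitly looks for adverse events, although only in a subset.
- The survey topic asks how health was affected as well as whether, so a harm can be reported there.
- The class route is offered weekly, and instructors are asked to report too. The physical therapist attends as scheduling allows and watches for safe participation. Follow-Up Care covers injuries, so a strain may surface before the survey does.
- Worse back pain and low mood are measured by the survey scales. Interviews ask what made participation difficult, and a sample of Veterans who did not complete most sessions is asked why they stopped.
- The exact survey wording is in Appendix E, which was not available and may already prompt for harm. That the Data Collection topic is the same item as the adverse-event question is a reasonable inference, but it is not stated.

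The illustration is also open to challenge. Both assumptions are chosen, and the masked scenario gives no credit to the weekly route. If soreness and fatigue are counted and half of Veterans have such an event, half masking gives 0.75^16 = 0.010, so the larger figures depend on low harm rates. Recording no harms in an arm is not a decision rule in the protocol.

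All of this limits the claim. It does not remove the core: each of these alternatives relies on the harm being volunteered, noticed or still present, and the chart-review trigger ignores the content of the answer.

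**Conclusion.** The point holds in limited form and stands on Monitoring Adverse Events alone. As described there, neither participant-reported route asks directly about harm, and the chart review is triggered by a missing survey or a blank answer. A harm in a Veteran who answers only with a benefit is therefore captured only if volunteered: in class, within the survey answer, or at interview, which lies outside the adverse-event plan.

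How many harms would be lost cannot be estimated from the documents. The 4-7% versus 21-29% comparison shows sensitivity under an assumed 15% harm rate and one-half masking; it is not a prediction. The conclusion depends on the protocol's description matching Appendix E. If that survey already contains a direct harm question, only the description and the trigger need clarifying. This is a weakness in harm ascertainment that is cheap to correct, and it does not invalidate the pilot's main aims.

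**What to change.** In Monitoring Adverse Events and the post-participation survey, for both arms:

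1. Keep the neutral item as a perception question.
2. Add a separate harm item with a yes/no line for each risk the protocol already lists: soreness, new or worse pain, fatigue, injury and emotional discomfort. Ask when each occurred and whether care was sought.
3. Name this item as the adverse-event question, and make a blank on it, or a missing survey, the trigger for the chart review.

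If Appendix E already has such an item, a sentence in Monitoring Adverse Events that identifies it and ties the trigger to it is enough.

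The cost is a few survey lines, about a minute per Veteran, and probably more reports of minor soreness. The item still relies on recall about a week after a 12-week program and leaves the weekly route as it is. An alternative is the same adverse-event chart review for all 32-40 Veterans, which removes the trigger problem at the cost of more staff time but finds only what was noted in the record.
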